7.5 PROHIBITED MEDICATIONS, TREATMENTS, AND PROCEDURES

The following medications, treatments, and procedures are prohibited at screening, and should result in a potential participant being deemed a screen failure:

- 1) Lithium use
- 2) Loop diuretic use
- 3) Interventions and medications that cause stones
 - a. Chronic corticosteroid use (>1 month)
 - b. Supplemental Vitamin C (>1 g daily)
- 4) Novel therapeutics for stone prevention

8 ASSESSMENT OF SAFETY

8.1 SPECIFICATION OF SAFETY PARAMETERS

Participation in the proposed study is completely voluntary. The research team will institute strict procedures to maintain confidentiality. All data and records generated during this study will be kept confidential and in accordance with institutional policies and HIPAA privacy policies. Study participants will be assigned a unique identification code that will be used as the sole identifier. Study participants and families will have direct access to the study team as a means to voice any questions, concerns, or reservations. Contact information will be provided at the time of consent. Should any specific concerns arise, the study team will intervene to address problems including, if needed, a change or discontinuation of study procedures. The appropriate institutional IRBs and DSMB will be informed of serious adverse events or protocol deviations, as outlined below.

8.1.1 DEFINITION OF ADVERSE EVENTS (AE)

Adverse Event

An adverse event (AE) is any untoward medical occurrence associated with the use of a study intervention in a study participant. An AE can, therefore, be any unfavorable and unintended sign (including an abnormal laboratory finding, for example), symptom, or disease temporally associated with the use of a pharmaceutical product or biologic. Diseases, signs, symptoms, or laboratory abnormalities already existing at the time of consent are not considered AEs unless they worsen (i.e., increase in intensity or frequency). Surgical procedures themselves are not AEs; they are therapeutic measures for conditions that require surgery. The condition for which the surgery is required may be an AE. Surgical procedures planned before randomization and the conditions leading to these measures are not AEs.

8.1.2 DEFINITION OF SERIOUS ADVERSE EVENTS (SAE)

Serious Adverse Event

An AE or SAE is considered serious if the investigator believes any of the following outcomes may occur:

1. Death.
2. Life-threatening AE: places the study participant, in the view of the investigator, at immediate risk of death at the time of the event as it occurred. It does not include an AE that, had it occurred in a more severe form, might have caused death.
3. Persistent or significant disability or incapacity or substantial disruption of the ability to conduct normal life functions.
4. Congenital abnormality or birth defect.
5. Requires inpatient hospitalization or prolongation of existing hospitalization with the following exceptions:
 - Preplanned (before the study) hospital admissions, unless the hospitalization is prolonged
 - Planned admissions (as part of a study)
 - Rehospitalizations (after discharge from index hospitalization) of less than 24 hours
 - Elective procedures
 - Emergency department visits

Important medical events that may not result in death, be life threatening, or require inpatient hospitalization may be considered a serious adverse event (SAE) when, based on appropriate medical judgment, they may jeopardize the study participant and/or require medical or surgical intervention to prevent one of the serious outcomes listed above. This determination is based on the opinion of the Investigator.

8.1.3 DEFINITION OF UNANTICIPATED PROBLEMS (UP)

Unanticipated problems are any event that is: unexpected in nature, frequency or severity; related or possibly related to participation in the research; or suggest that the risk of harm to study participants is increased.

8.2 CLASSIFICATION OF AN ADVERSE EVENT

8.2.1 ASSESSMENT OF ADVERSE EVENT SEVERITY

The determination of AE severity rests on medical judgment of a medically qualified investigator. The severity of AEs will be graded using the following definitions:

- **Mild:** Awareness of sign, symptom, or event, but easily tolerated.
- **Moderate:** Discomfort enough to cause interference with usual activity and may warrant intervention.

- **Severe:** Incapacitating with inability to do usual activities or significantly affects clinical status and warrants intervention.

8.2.3 EXPECTEDNESS

Any adverse event, the specificity, nature, or severity of which is not consistent with the underlying disease process, will be considered an unexpected AE. AEs that are expected based on the underlying disease process are worsening renal function, ureteral stricture disease, or obstructed urinary infection.

8.3 TIME PERIOD AND FREQUENCY FOR EVENT ASSESSMENT AND FOLLOW-UP

The site Investigator is responsible for monitoring the safety of participants enrolled into the study at the study sites. Monitoring for AEs and SAEs will occur from informed consent to month 24. Adverse events will be queried as part of periodic email/telephone follow-up with participants.

8.4 REPORTING PROCEDURES

8.4.1 ADVERSE EVENT REPORTING

For this study, non-serious AEs will not be collected on the safety reporting page of the eCRF, but should be documented in the source documents and followed according to local standard of care. Investigators are also responsible for promptly reporting AEs to their reviewing IRB in accordance with local requirements.

8.4.2 SERIOUS ADVERSE EVENTS

SAEs occurring from *informed consent* to month 24 will be captured on the SAE eCRF.

8.4.3 SERIOUS ADVERSE EVENT REPORTING

All SAEs, whether or not deemed intervention related or expected, must be reported by the investigator or qualified designee within 1 working day of first becoming aware of the event. The investigator or qualified designee will enter the required information regarding the SAE into the appropriate module of the eCRF. If the eCRF system is temporarily unavailable, the event, including the investigator-determined causality to study intervention should be reported via the back-up paper SAE form to the SDRC. Upon return of the availability of the electronic data capture (EDC) system, the SAE information must be entered into the eCRF.

When additional relevant information (i.e., final diagnosis, outcome, results of specific investigations, etc.) becomes available, the Investigator will record follow-up information according to the same process used for reporting the initial event as described above. The Investigator will follow all reportable events until resolution, stabilization or the event is otherwise explained.

The SDRC will follow all SAEs until resolution, until stabilization, until otherwise explained or until the last subject completes the final follow-up, whichever occurs first. The SDRC will report all SAEs to the Data Safety Monitoring Board (DSMB) chair in accordance with the DSMB Charter.

8.4.4 UNANTICIPATED PROBLEM REPORTING

AEs that meet the criteria of serious, related to study intervention, and unexpected, qualify for expedited reporting to the IRB. The Investigator will assess all SAEs occurring at his/her clinical center and evaluate for “unexpectedness” and relationship to study procedures or intervention. The Investigator is required to complete and submit a report for the events identified as serious, study procedure or intervention related, and unexpected and submit the report to their reviewing IRB in accordance with local requirements.

A copy of this report should be kept at the clinical center and also forwarded to the SDRC within the same timeline used for reporting to regulatory authorities.

8.4.5 EVENTS OF SPECIAL INTEREST

Episodes of hyponatremia requiring medical attention (e.g., hospitalization) will be reported as a Serious Adverse Event, as described in 8.4.2.

8.4.6 REPORTING OF PREGNANCY

During the course of the trial, all study participants of childbearing potential will be instructed to contact their Investigator immediately if they become pregnant. Pregnancy occurring during the study period, although not considered a serious adverse event, must be reported within the same timelines as a Serious Adverse Event. The pregnancy will be recorded on the appropriate pregnancy form in the EDC database. The pregnancy will be followed until final outcome. Any associated AEs or SAEs that occur will be recorded in the EDC database.

8.5 SAFETY OVERSIGHT

The Investigator is responsible for monitoring the safety of participants enrolled into the study at their clinical center. The SDRC will follow all SAEs until resolution, until stabilization, until otherwise explained or until the last subject completes the final follow-up, whichever occurs first. The SDRC will report all SAEs to the Data Safety Monitoring Board (DSMB) chair in accordance with the DSMB Charter.

The DSMB will review detailed safety data approximately every 6 months throughout the study.

9 CLINICAL MONITORING

SDRC will employ a “risk-based monitoring” strategy that ensures human subject protection and data quality are held in the utmost regard. Data-Driven Trial Management (DDTM) is a targeted analysis-based surveillance effort designed to proactively minimize risk and improve quality.

SDRC focuses on a simple and pragmatic project management strategy based on the following quality by design principles with human subject protection and data quality and integrity as the foundation of project planning and execution: 1) the correct subjects are enrolled and consented, 2) acceptable treatment adherence is met, 3) complete efficacy data is ascertained, 4) complete safety data is ascertained, and 5) good clinical practices (GCP) are followed.

Integrated SDRC systems support our RBM strategies allowing us to closely monitor and track agreed upon key risk indicators and follow-up quickly with necessary interventions. In addition, our systems support focused monitoring activities, including source data verification, online drug accountability, and regulatory document tracking.

Based on our significant data quality experience, the SDRC has established strategies and supporting tools to deliver high quality data that is critical for all trials including long term, event driven trials. By integrating the varied data sources and providing seamless reporting of trial data status, we enable the team to proactively manage trials.

As part of a concerted effort to follow the study in a detailed and orderly manner in accordance with established principles of GCP and applicable regulations, a SDRC team member will maintain frequent telephone and written communication.

10 STATISTICAL CONSIDERATIONS

10.1 STATISTICAL AND ANALYTICAL PLANS

The statistical team at SDRC will perform the statistical analyses described in this section. An Intention-to-treat analysis will be performed and will serve as the primary analysis for the primary objective in this study. The Intention-to-treat cohort will include all randomized study participants.

In a separate document, a statistical analysis plan (SAP) will be developed by the SDRC team to include a comprehensive description of the statistical methods and analyses for the primary manuscript as well as the final study report. Prior to analysis, study population details, including the number of sites, the number of study participants in each study arm, and the number of study participants lost to follow-up will be described. Data for all randomized study participants, whether or not they completed all protocol requirements, will be included for analysis.

10.2 STATISTICAL HYPOTHESES

The primary hypothesis of the time-to-first symptomatic stone will be tested under Cox proportional hazards model as:

$$H_0: \text{HR} = 1.0 \text{ vs. } H_a: \text{HR} \neq 1.0$$

Other hypotheses of interest that the intervention will increase fluid intake (goal urine output at least 2.5 L daily) will lead to a fewer symptomatic and asymptomatic stone events over 2 years of study period. In addition, we will test time-to-recurrent symptomatic stone events.

10.3 ANALYSIS DATASETS

Data from all randomized study participants, regardless of whether or not they completed all protocol follow-up requirements, will be included for analysis. The analysis population will be the intent-to-treat (ITT) population. In addition, a per-protocol analysis will be performed. The analysis population for the per protocol analysis will consist of participants in the ITT population except those who have had a major protocol deviation.

10.4 DESCRIPTION OF STATISTICAL METHODS

10.4.1 GENERAL APPROACH

The primary analysis will be conducted by intention-to-treat principles. The analysis cohort for this study consists of all randomized study participants regardless of whether the study participant received the randomly assigned intervention strategy. All study participants who provide informed consent and who are randomized will be included in the analyses. For those study participants who are lost to follow-up, or who drop out of the study, the analyses will include all data up to the point of their last data collection whenever applicable. Safety data will be collected on all randomized study participants. All statistical analysis will be tested at two-sided nominal significance level of 0.05. If missing data constitute <2% of observations, the analysis will utilize single imputation (mean for continuous variables, mode for categorical variables). If missing data are >2% of observations, then the approach to missing data will depend on checks of the missing-at-random assumption, and will be detailed in the Statistical Analysis Plan.

10.4.2 ANALYSIS OF THE PRIMARY EFFICACY ENDPOINT(S)

The primary endpoint (symptomatic stone event) will be analyzed as a time-to-event outcome with a log-rank test⁴² or equivalently, the Cox proportional hazards model,⁴³ the approach used for calculating sample size requirements. Kaplan-Meier estimates⁴⁴ of cumulative event rates as a function of follow-up time will be calculated and displayed. In addition, stratified Cox proportional hazards model will be conducted where the strata are those used in the randomization scheme. Furthermore, data collected on subsequent recurrent events of symptomatic stone will be analyzed using the Andersen-Gill model⁴⁵ (with adjustment for correlation within a study participant) and/or negative binomial regression.

A symptomatic stone event will be defined as stone passage, symptomatic stone requiring procedural intervention, or any asymptomatic stone undergoing procedural intervention. A pre-specified sensitivity analysis of the definition of symptomatic stone event will include stone passage, symptomatic stones requiring procedural intervention, and asymptomatic stones undergoing procedural intervention that meet at least one of the following criteria: stone size at least 4 mm in any dimension, mobile stone, hematuria or recurrent urinary tract infection. An additional pre-specified sensitivity analysis will exclude any symptomatic stone events that occur within 30 days of randomization.

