4.2 STUDY ENDPOINTS

4.2.1 PRIMARY ENDPOINT

Symptomatic kidney stone recurrence. A symptomatic stone will be defined as any of the following:

1. Stone passage observed and/or captured by the study participant
2. Procedural intervention for symptomatic stone
3. Any procedural intervention for removal of asymptomatic renal or ureteral stone (See section 10.4.2 for analytic details)

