4.3 RANDOMIZATION

Study participants will be randomized in a ratio of 1:1 to one of two parallel study groups, designated as “intervention” and “control”. Randomization will be stratified within a clinical center by (adult vs. adolescent) and (first time vs. recurrent stone former). Randomization will be conducted at the clinical center level in blocks of variable size to minimize potential confounders related to differences in site-based care practices. The randomization will be performed with the use of an internet-accessible integrated randomization module in the EDC system.

The randomization scheme will be generated by a statistician at SDRC. This statistician will not be a part of the analytic team for the study results, to minimize the possible introduction of bias into study results.

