Behavioral Intervention Program	none	
Months 0-6 (Induction):
 
 • Daily financial incentive for success at meeting fluid intake goal via water bottle (FI possible 100% of days) • Structured Problem Solving (SPS) 
 ○ Non-adherence trigger if fluid goal was achieved less than 80% of days over two weeks (i.e., >3 days where fluid goal was not met during 14 day period) for two 14-day assessment periods. • SPS “Booster” (intensified counseling) 
 ○ Non-adherence trigger if fluid goal was achieved less than 80% of days over two weeks (i.e., >3 days where fluid goal was not met during 14 day period) for two 14-day assessment periods following initial SPS. 
Months 7 -12 (Consolidation):
 
 • Daily financial incentive for success at meeting fluid intake goal via water bottle possibility of receiving incentive for 80% of days [24] in 1 month period) • Structured Problem Solving (SPS) 
 ○ Non-adherence trigger if fluid goal was achieved less than 80% of days over two weeks (i.e., >3 days where fluid goal was not met during 14 day period) for two 14-day assessment periods. • SPS “Booster” (intensified counseling) 
 ○ Non-adherence trigger if fluid goal was achieved less than 80% of days over two weeks (i.e., >3 days where fluid goal was not met during 14 day period) for two 14-day assessment periods following initial SPS. 
Months 13 – 18 (Tapering):
 
 • Taper daily financial incentive (75% of days at month 13 and 15% of days at month 18) • Self-selected/low touch intervention(s) 
 ○ Text/phone reminders ○ Commitment contract ○ Social intervention (e.g., team) 
Months 19-24 (Maintenance):
 
 • Self-selected/low touch intervention(s) 
 ○ Text/phone reminders

	Control	Intervention
		
 ○ Commitment contract ○ Social intervention (e.g., team) ○ Feedback of adherence
Stone-directed pharmacological or urological care	Per primary stone treating provider	Per primary stone treating provider

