10.5 SAMPLE SIZE

Conservative power calculations are based on symptomatic recurrence rates reported by Rule and colleagues.⁴⁹ The following assumptions are incorporated into the power calculation:

- 1) Unit of randomization: patient
- 2) Equal randomization ratio (1:1)
- 3) 15% event rate (composite of USD recurrence) over 2 years in control arm
- 4) 30% relative risk reduction for intervention arm (HR = 0.7)
- 5) 20% attrition rate (dropouts, loss to follow up)
- 6) Two-sided alpha of 0.05, log-rank test for time to event
- 7) 2 year follow up

$N = 821$ per arm (total = 1642 study participants) provides 80% power to detect the pre-specified relative risk. Sample size calculations were carried out using SAS (PROC POWER) version 9.4 (SAS Institute Inc., Cary, NC).

Study participants will be recruited from the 4 Clinical Centers over a 2-year period.

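### The primary log-rank/Cox test leaves out the randomization strata; making the already planned stratified analysis primary would cost little and guard against lost power

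*Combined protocol and SAP*

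**What the plan says.** Section 4.3: "Randomization will be stratified within a clinical center by (adult vs. adolescent) and (first time vs. recurrent stone former"). It adds that randomizing by center in blocks is meant "to minimize potential confounders related to differences in site-based care practices". With the six primary centers named in the Protocol Summary and section 7.1.1, this makes 6 × 2 × 2 = 24 strata.

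Section 10.4.2: "The primary endpoint (symptomatic stone event) will be analyzed as a time-to-event outcome with a log-rank test", with a Cox model offered as equivalent and described as the basis of the sample size. Section 10.2 agrees: "The primary hypothesis of the time-to-first symptomatic stone will be tested under Cox proportional hazards model". So does section 10.5: "Two-sided alpha of 0.05, log-rank test for time to event". None of the three names strata.

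Later in the same paragraph of section 10.4.2: "In addition, stratified Cox proportional hazards model will be conducted where the strata are those used in the randomization scheme". The analysis that matches the design is therefore pre-specified, but not as the one that decides the trial. Section 10.1 defers full methods to a separate SAP that is not supplied.

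**The concern.** Stratified blocks balance the arms within each stratum. If the strata are prognostic, the treatment comparison varies less from trial to trial than the unstratified log-rank variance assumes. The test then rejects less often than its nominal level under the null and loses power under the alternative. Nothing is biased in favor of the intervention.

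The documents do not say how far recurrence differs between strata, but they give reasons to expect some difference. Section 4.3 cites variation in care between sites. Section 4.2.1 counts as a primary event "Any procedural intervention for removal of asymptomatic renal or ureteral stone", while section 6.1.1 leaves urological care "Per primary stone treating provider". A center's readiness to operate on silent stones thus feeds directly into the endpoint. Section 10.4.8 also lists center, age group and stone history among the subgroups of interest.

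At stake are a few points of power at most, and clarity about which of two planned results governs if they fall on different sides of 0.05.

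**Working it through.** **1. The plan's own sample size.** Inputs from section 10.5: HR 0.7, 15% control risk over 2 years, 20% attrition, two-sided alpha 0.05, 80% power, 1:1 allocation, N = 1,642.

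- Events needed (Schoenfeld): 4 × (1.960 + 0.842)² / (ln 0.7)² = 4 × 7.849 / 0.1272 = 247.
- Exponential hazards per year: control -ln(0.85)/2 = 0.0813; intervention 0.7 × 0.0813 = 0.0569.
- If follow-up runs uniformly from 2 to 4 years (2-year accrual, common closing date), event probabilities are 21.5% and 15.6%, mean 18.6%. Then 247/0.186 = 1,328, and 1,328/0.8 is about 1,661, within 1.2% of 1,642. The stated N is reproduced on this reading.
- If everyone is followed for 24 months, as the Protocol Summary says, the probabilities are 15% and 1 - 0.85^0.7 = 10.8%, and about 2,400 participants would be needed.
- With 24-month censoring and exponential dropout of 20% over 2 years, 1,642 participants give about 190 events. Power is Φ(√190/2 × 0.357 - 1.960) = Φ(0.498) = 69.1%.

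This is why base power below is near 68% and not 80%. It is a separate issue and carries no weight here.

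**2. Main simulation.** 20,000 trials per scenario, N = 1,642, six equal centers, 24 strata, both tests run on the same data at two-sided 0.05. Mean control risk is 15% at 2 years, within-stratum HR is 0.7 (or 1 for type I error), dropout is 20%, and follow-up is censored at 24 months. Assumed, because the documents do not give them: blocks of 4 or 6, 50% recurrent formers, 15% adolescents, age not prognostic, normal center effects on the log hazard, and the prognostic strengths themselves.

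| Recurrent-vs-first HR; center SD | Power, unstratified → stratified | Change (points) | Type I error, unstratified / stratified | Mean estimated HR, unstratified / stratified |
|---|---|---|---|---|
| 1; 0 | 68.3% → 68.2% | -0.1 | 5.1% / 5.1% | 0.699 / 0.699 |
| 1.5; 0.2 | 68.0% → 68.3% | +0.3 | 4.9% / 5.1% | 0.699 / 0.698 |
| 2; 0.3 | 67.5% → 68.1% | +0.7 | 4.6% / 5.0% | 0.702 / 0.699 |
| 3; 0.5 | 65.9% → 68.3% | +2.4 | 4.3% / 5.0% | 0.706 / 0.698 |
| 3; 0.8 | 62.6% → 66.7% | +4.0 | 3.7% / 4.8% | 0.715 / 0.700 |

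Changes were computed before rounding. The Monte Carlo SE is 0.09 to 0.16 points for each change and about 0.15 points for type I error.

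**3. Other layouts** (change in power, same five rows):

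- Unequal centers (30, 25, 15, 12, 10, 8%): -0.4, +0.3, +0.8, +2.3, +4.1.
- Six centers plus one level for outside locations (10% of participants, assumed): -0.2, +0.3, +0.9, +2.2, +4.3.
- Control risk raised to 19.9%, giving about 255 events and 80.7% base power: -0.1, +0.2, +0.8, +2.5, +4.4.

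**4. Sparse strata.** With 15% adolescents, the 12 adolescent strata average 1,642 × 0.15 / 12 = 20.5 participants. At 190/1,642 = 11.6%, that is about 2.4 events each. Even so, fewer than 0.1 events per trial were lost to risk sets containing only one arm, in every layout.

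**5. Separate simulation with other settings.** In the top two settings age was also prognostic (adolescent HR 1.5, then 2), and the extreme case was stronger (recurrent HR 5, SD 0.8).

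| Setting | Change in power, 24 months | Change in power, 2–4 years | Unstratified type I error, 24 months / 2–4 years |
|---|---|---|---|
| None | -0.3 | -0.7 | 4.8% / 5.3% |
| HR 2; 0.3 | +0.8 | +1.1 | 4.6% / 4.6% |
| HR 3; 0.5 | +1.8 | +2.7 | 4.4% / 3.9% |
| HR 5; 0.8 | +5.7 | +8.4 | 3.5% / 3.2% |

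Stratified type I error stayed between 4.8% and 5.3% throughout.

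The mechanism can be checked directly. If the unstratified Z has standard deviation s under the null, its type I error is 2Φ(-1.960/s). The 24-month runs gave s = 0.985, 0.966 and 0.924 for the last three rows, hence 4.7%, 4.2% and 3.4%, close to the simulated 4.6%, 4.4% and 3.5%.

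**6. Disagreement between the tests.** In the main simulation they fell on different sides of 0.05 in 1.7% to 2.3% of trials with no to moderate prognosis, and in 3.8% to 5.4% with strong to extreme prognosis.

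**The case against.** The plan already contains the stratified Cox model, so only the primary label is in question. The unstratified test never inflates type I error, matches the stated sample-size method and is a defensible choice. The gain is negligible up to moderate prognosis. Losses of 2 to 4 points need a threefold hazard for recurrent formers together with a center SD of 0.5 to 0.8, so that centers one SD above and below the mean differ exp(2 × 0.5) = 2.7-fold to exp(2 × 0.8) = 5-fold in hazard. Nothing in the documents establishes differences of that size. The unseen SAP may settle the matter. Finally, the documents do not say how participants from outside the primary centers are stratified at randomization, and section 10.5 speaks of 4 centers where the Protocol Summary and section 7.1.1 say 6, so the analysis strata might not match the randomization strata exactly.

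Most of this stands as a limit on the size of the point. It does not show that the present ordering is better. The price of stratifying when the strata are not prognostic is 0.1 to 0.4 points in the main simulation and 0.7 at most in the other, against larger losses the other way if they are. Pooling outside locations is at worst a coarser stratification, and the test remains valid.

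**Conclusion.** The concern holds as a recommended improvement, not as an error. The primary test as written does not use the strata that the trial randomizes by, and it is conservative if center or stone history predicts recurrence.

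The size rests on assumed prognostic strengths. Up to a recurrent-versus-first hazard ratio of 2 and a center SD of 0.3, the choice moves power by -0.7 to +1.1 points across all runs, which is close to nothing. At a hazard ratio of 3 and SD of 0.5 it is worth about 2 to 3 points, and at SD 0.8 about 4. Only the most extreme setting tried (hazard ratio 5, prognostic age, SD 0.8) gives 6 to 8. The direction is secure; the magnitude in this trial is unknown. The conclusion falls away if the separate SAP already makes the stratified test primary.

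**What to change.** Before unblinding, amend section 10.4.2 and the SAP as follows:

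- Make the log-rank test stratified by clinical center, age group and stone history the single primary test.
- Report the hazard ratio from the matching stratified Cox model and label it a within-stratum hazard ratio.
- Keep the unstratified log-rank/Cox analysis as supportive.
- State how participants from outside the primary centers were stratified at randomization, and treat all such locations as one center level in the analysis.
- Bring the number of centers in section 10.5 into line with the Protocol Summary and section 7.1.1.
- Optionally, merge the two age groups within center and stone history where events are few, with the threshold fixed in advance and events counted blinded to arm. Merging where either age stratum had fewer than 5 events kept power within 0.1 point of no merging with six equal centers.

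The cost is wording only; sample size and data collection are unchanged. The statistical price is the small power loss given above if the strata turn out not to be prognostic. The estimand becomes a within-stratum hazard ratio, which differs little in practice: 0.699 against 0.702 unstratified at moderate prognosis, and 0.700 against 0.715 in the extreme case of the main simulation.
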